neural activity and dopamine metabolism in basal ganglia regions including the dorsal striatum as assessed by a variety of neuroimaging strategies following several inflammatory stimuli including Interferon-alpha, typhoid vaccination and endotoxin^{51-53, 59, 123} Administration of inflammatory stimuli have also been shown to lead to depressive symptoms, including psychomotor retardation as well as objective measures of psychomotor slowing.^{52,124, 125} In a recent study of the role of inflammation in patients with depression, IL-6, IL-10, and MCP-1 were all shown to be associated with objective measures of psychomotor slowing¹²⁶. These inflammatory markers have all been demonstrated to be aberrant in patients with schizophrenia⁶¹. Psychomotor retardation has been described in patients with schizophrenia and is considered to be a negative symptom of the disorder. As such, we will plan to test the hypothesis that inflammation also decreases activation of the dorsal striatum and its associated circuitry, leading to decreased objective measures of psychomotor speed and negative symptoms in schizophrenia.

A range of neuropsychological assessments will be used to probe basal ganglia function and will be associated with inflammation status as noted above. Assessments will lie along a continuum, progressing from more purely motor tasks (such as finger tapping) which assess circuitry within the basal ganglia to those that involve motor speed with increasing cognitive demand and cortical participation (e.g. the Digit Symbol Task). In addition, we will administer a test of procedural memory, with minimal processing speed or reaction time demands, that has been shown to be sensitive to dysfunction in the basal ganglia, without the executive demands associated with tests of frontal lobe function. Every effort will be made to match groups on the basis of demographic factors affecting test performance, such as age, education level, gender and ethnicity. These factors can significantly influence neuropsychological test results and while relatively small variations between groups can be handled through addition of covariates to statistical analyses, more significant differences in-group composition will threaten the integrity and interpretation of the results.

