Finger Tapping Task (FTT): This task uses a specially adapted tapper that the subject is asked to tap as fast as possible. The subject is given 5 consecutive 10-second trials for the preferred and non-preferred hands. The FTT is designed to assess subtle motor impairment and found to be altered in subjects with basal ganglia disorders and lesions.¹⁰⁴

Reaction Time Task (CANTAB): This reaction time test includes simple and choice reaction time tasks and is divided into 5 stages requiring increasingly complex chains of responses and providing distinction between reaction (or decision) time and movement latencies. Movement times on the CANTAB reaction time task have been slowed during IFN- α treatment and correlated with IFN-alpha-induced depression and fatigue.¹⁰⁵

Trail Making Test Part A (TMT-A): The Trail Making Test-A is a timed task that provides information on motor function and speed of processing.¹⁰⁶ Previous studies have indicated that performance of TMT-A significantly correlates with reduced caudate volumes in older persons with depression.¹⁰⁷

Digit Symbol Substitution Task (DSST): The DSST is a subtest of the Wechsler Adult Intelligence Scale and involves graphomotor speed, visual scanning and memory, with about half of the variance being accounted for by graphomotor speed, a third by visual scanning and 4-5% by memory.¹⁰⁸ Performance on the Digit Symbol Test has been found to correlate with subcortical (caudate) atrophy in disorders involving the basal ganglia.¹⁰⁵

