Effort-Expenditure for Rewards Task (EEfRT): The EEfRT task is a multi-trial game in which participants are given an opportunity on each trial to choose between two different task difficulty levels in order to obtain monetary rewards.¹⁰⁹ For all trials, participants make repeated manual button presses within a short period of time. Each button press raises the level of a virtual "bar" viewed onscreen by the participant. Participants are eligible to win the money allotted for each trial if they raise the bar to the "top" within the prescribed time period. Each trial presents subjects with a choice between two levels of task difficulty, a 'high effort' and 'low effort' task that require different amounts of speeded button pressing. Reward magnitudes for the high effort task will vary between \$1 and \$10, while reward magnitudes for the low effort task remain constant (between \$0.50 and \$1.00). The reward magnitudes will be decided at the discretion of the PI. Trials will also vary in terms of 3 levels of probability of winning the amount associated with the choice selected. Subjects participate in the task for approximately 20 minutes and the first 50 trials are used for analysis. Because of the requirement for rapid button presses for a long period of time, we will exclude participants who report chronic pain in their wrists/hands and or those who have wrist/hand injuries, such as Carpal Tunnel Syndrome. At the discretion of the PI, the EEfRT may be repeated after the neuroimaging scan.

Neuroimaging Tasks:

The PI will choose which of these fMRI tasks will be performed at the fMRI study visits.

Monetary Incentive Delay (MID) Task: Assessment of reward anticipation will be achieved using the MID task.^{26,110-112} Briefly, during this task participants have the opportunity to win or lose money by making a rapid button press in response to a target visual stimulus. The primary epoch of interest is the “anticipatory delay” – a period of ~2000ms that occurs after participants have been informed how much money they can win or lose on a given trial, but prior to the presentation of the target. This epoch has repeatedly been associated with robust ventral striatal activity.^{26,110,113-114} Participants will complete 2 functional runs of between 50 and 200 trials each (the number of trials will be decided at the discretion of the PI), with evenly distributed reward magnitudes between \$0.20 and \$10.00, to be decided by the PI.

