fMRI-adapted version of the EEfRT task: Assessment of effort-based decision making will be assessed using the EEfRT task.¹⁰⁹ During each trial, subjects are presented with a choice between two levels of task difficulty, a High Effort option and a Low Effort option. Unlike in the behavioral version of the task, subjects will not be required to make button presses during the scan. The reward magnitude for a No Effort option remains constant, while the reward magnitude for the High Effort option varies from \$1.00 to \$10.00. Additionally, the amount of effort required for the High Effort option will vary between 20%, 50%, 80% and 100% of the subject's maximum effort (set for each individual prior to scan).

Reinforcement Learning (RL) Task: Trials for this task involve a 3s cue presentation during which subjects choose between two abstract stimuli, followed by an exponentially jittered delay, and then a 3s feedback presentation with positive (monetary win), negative (monetary loss) or neutral outcomes. This task has been shown to robustly activate the ventral striatum in response to prediction errors.

Safety and Tolerability

Adverse Event Recording: All adverse events will be coded in standard MedDRA terms (Version 14.1), and whether events are expected and study-related will be determined by the study PI. In addition, severity and start and end dates will be recorded as well as any evidence of unanticipated problems. This information will be provided to the Department of Psychiatry and Behavioral Sciences DSMB and IRB annually as described in the Human Subjects Section.

Laboratory Variables

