Objective 2: Descriptive statistics will be used to characterize the mean, standard deviation, and standard error for each of these clinical and behavioral measures. For the EEfRT, proportion of hard-task choices across each level of probability as well as the difference between the proportions of hard task choices in low and high reward probabilities (effort allocation) will be calculated. Lower proportions of hard task choices indicate decreased motivation for monetary rewards. A larger difference in the proportion of hard task choices reflects more effort allocation. Regression analyses will be conducted to examine the relationship between task performance and concentrations of inflammatory markers (beginning with CRP). Regression analyses examining the relationship between changes in functional connectivity (Z scores) obtained using fMRI and changes in behavior and neuropsychological performance will also be conducted. In cases where data are not normally distributed, we will use standard transformation procedures to achieve normality, and/or use non-parametric tests of significance. The same covariates and data reduction strategies described above will be used in these analyses.

Objective 3: Formal mediation analysis will be conducted to assess whether functional connectivity mediates

the relationship between inflammation (as measured by inflammatory marker concentrations – beginning with CRP) and behavior (clinical ratings and objective measures, as described above). Bootstrapping will be used to provide an empirical estimate of the sampling distribution for indirect effects and will be used to generate confidence intervals for the purpose of inferential testing. A model of moderated-mediation will also be tested to assess whether mediation pathways are influenced by the presence of high vs. low baseline inflammation. Path analysis will be implemented using macros developed by Preacher and Hayes (<http://quantpsy.org/medn.htm>), which enable inclusion of covariates as well as possible moderators.

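### On the behavioural EEfRT, fewer hard-task choices are read only as lower motivation, although the protocol expects inflammation to slow motor speed and plans no motor-speed adjustment

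*Combined protocol and SAP*

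**What the plan says.** Section 7, Objective 2 derives two kinds of EEfRT outcome: "proportion of hard-task choices across each level of probability as well as the difference between the proportions of hard task choices" at low and high reward probability, the latter called effort allocation. It then gives the hard-choice proportion a single meaning: "Lower proportions of hard task choices indicate decreased motivation for monetary rewards". EEfRT performance is regressed on inflammatory markers, starting with CRP.

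The EEfRT description in section 5 says the high- and low-effort options are tasks "that require different amounts of speeded button pressing". A trial can pay out only if the on-screen bar is filled before time runs out. People with chronic wrist or hand pain, or with such injuries, are excluded because of the pressing.

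The Neurocognitive Assessments text in section 5 links inflammation to slower psychomotor speed and sets out a hypothesis for this sample: inflammation lowers dorsal striatal activation, "leading to decreased objective measures of psychomotor speed and negative symptoms in schizophrenia". Motor speed is measured by the Finger Tapping Task: "This task uses a specially adapted tapper that the subject is asked to tap as fast as possible".

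The covariates under Objective 1 are BMI, age, sex, education, nicotine use, antipsychotic dose, other medication and depression, to be used as appropriate. Objective 2 adopts the same list. It contains no motor-speed measure.

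**The concern.** The exposure, inflammation, is expected by the protocol itself to affect a capacity that the hard option demands. Someone who presses slowly has less chance of filling the bar in time, so the hard option is worth less to that person. Choosing it less often can then be sensible behaviour by a fully motivated patient, yet the plan would report it as reduced motivation for money.

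What is at stake is the interpretation of one result. Hypothesis 2 is worded as an association, so a CRP-EEfRT association that runs through slowing would be a real association. The error would lie in attributing it to motivation. The EEfRT is the only objective motivation task named under Objective 2, so the objective half of the motivation claim leans on it. Objective 3 inherits the ambiguity where EEfRT is the outcome. Its mediator is striatal connectivity, and the seeds include dorsal as well as ventral striatum, so a motor route could be described as a motivational one.

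**Working it through.** **The plan's own figure.** The Power Analysis in section 7 claims more than 80% power for r = 0.5 with N = 100 at two-tailed 0.05. By Fisher's z, power = Φ(atanh(r)·√(N−3) − 1.96). Here atanh(0.5)·√97 = 5.41, and Φ(5.41 − 1.96) = 99.97%, which agrees. At this N the smallest significant |r| is about 0.197, so quite modest associations will reach significance.

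**Model for the concern.** Suppose CRP has no effect on motivation. Let a be the size of the (negative) CRP-speed correlation and b the speed-choice correlation. If speed is the only link, the implied CRP-choice correlation is −a·b. The documents give neither a nor b, so the values below are assumptions and are shown as a range. The chance of a two-sided significant result is Φ(m − 1.96) + Φ(−m − 1.96), with m = atanh(a·b)·√97.

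| a / b (assumed) | implied r | m | chance, formula | chance, simulated (4,000 trials) |
|---|---|---|---|---|
| 0.2 / 0.3 | −0.06 | 0.59 | 9.1% | 9.5% |
| 0.3 / 0.4 | −0.12 | 1.19 | 22.1% | 22.3% |
| 0.4 / 0.5 | −0.20 | 2.00 | 51.5% | 51.7% |

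With weaker paths (0.2/0.2, r = −0.04) the chance is only about 7%, little above the nominal 5%.

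**Effect of adjusting for tapping.** Assume tapping measures motor speed with reliability 0.8. The tapping correlations are then a·√0.8 with CRP and b·√0.8 with choice. The partial correlation has absolute value (ab − 0.8ab)/√[(1 − 0.8a²)(1 − 0.8b²)]. For 0.4/0.5 this is 0.04/√(0.872 × 0.800) = 0.048. Using √96 in place of √97, the chance of significance is about 7.6%. The simulated rates for the three rows are 5.2%, 5.4% and 7.9%, so adjustment removes most but not all of the motor path.

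**Cost of adjusting when the effect is truly motivational.** Assume CRP-motivation r = −0.4, motivation-choice r = 0.7 and no motor effect. Then the CRP-choice r is −0.28 and power is 81%. If tapping itself correlates 0.5 with motivation, its correlations are −0.20 with CRP and 0.35 with choice. The partial correlation is (−0.28 + 0.07)/√(0.96 × 0.8775) = −0.229, and power falls to 63%. If tapping correlates 0.3 with motivation, the partial correlation is −0.263 and power is 75%.

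**Effort allocation.** If slowing lowers hard choices by the same amount d at both probability levels, the difference is (p_high − d) − (p_low − d) = p_high − p_low, and d cancels. Unequal slowing effects, for example a floor at low probability, would not cancel fully.

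**The case against.** Several points on the other side stand.

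- A reader might infer that failed hard trials are counted as low motivation. They are not. Objective 2 scores choices, so slowing can act only through avoidance of the hard option, which is a narrower route.
- A reader might infer that motor slowing could produce the whole Hypothesis 2 result. The documents do not support that: Hypothesis 2 also covers clinical measures, and PANSS, BNSS, SHAPS and MAPS-SR need no speeded pressing.
- A reader might conclude that the EEfRT cannot support any motivation claim. That is too strong. The effort-allocation score is planned and probably less exposed. Tapping, CANTAB movement time and Trail Making A are scheduled. The scanner version removes the presses and scales effort to each person's maximum, although the investigator may substitute another task for it.
- The behavioural task is not shown to be uncalibrated. Its description is a summary that gives no press counts or time limits and says nothing on individual calibration.
- The covariate list is open-ended, and age, BMI, antipsychotic dose and depression may absorb part of the motor path. The calculation includes none of them.
- The protocol counts psychomotor retardation as a negative symptom, so speed may lie on the causal path of interest.

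None of this removes the core. An open-ended list does not pre-specify a motor-speed adjustment, the hand-injury exclusion does not cover central slowing, and the stated reading concerns motivation for monetary reward rather than negative symptoms in general.

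**Conclusion.** The concern holds for the hard-choice measure of the behavioural EEfRT in Objective 2, and in Objective 3 where EEfRT is the outcome. The plan attaches one meaning to fewer hard choices, while its own psychomotor hypothesis supplies another that no listed covariate addresses.

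How much this matters cannot be settled from the documents. Over the three assumed settings the chance of a significant CRP-EEfRT association without any motivational effect runs from about 9% to 52%. That range rests on two correlations that are not given, on speed being the only link, and on no other covariates being in the model. This is an inexpensive improvement to the analysis and its reporting; it does not invalidate the objective.

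**What to change.** Pre-specify, in section 7, a sensitivity analysis that adds finger-tapping speed as a covariate to the CRP-EEfRT regression and to the mediation model with EEfRT as outcome. Report it beside the unadjusted estimate and the effort-allocation result. If the hard-choice association shrinks materially, state that motor slowing cannot be excluded and do not attribute the association to motivation alone.

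The cost is SAP wording and use of a scheduled assessment, with three limits:

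- Tapping partly reflects effort and may be on the causal path. The adjusted estimate is conservative and less powerful, and should not be a pass/fail condition for the motivation claim.
- Tapping may be missing, because section 5 (Part A, Enrollment) lets the investigator waive assessments.
- Figure 3 places the EEfRT at screening and the neurocognitive battery at Visit 3 by default, so the two may be measured at different visits. Report the number with both and the interval between them.

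Hard-task completion rate should not be a covariate: it is undefined for a patient who chooses no hard trials, and it depends on effort. It can be reported descriptively. The task should not be altered mid-study, since that would split the sample across two versions of the outcome.

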The proposed research represents the first study to address the potential role of the immune system and inflammation in negative symptoms of schizophrenia, specifically by testing the hypothesis that inflammation affects fundamental reward circuitry in the ventral striatum leading to deficits in motivation and reward processing. Negative symptoms are highly resistant to treatment and have a major impact on functional outcomes. Therefore, understanding novel mechanisms by which negative symptoms occur will allow the development of innovative therapeutic strategies to improve quality of life and treatment outcomes in patients with this disorder. Moreover, given that inflammation can be measured in peripheral blood, the opportunity exists to target immune-based therapies to specific subpopulations of schizophrenia patients, thereby allowing a more personalized approach, supporting precision medicine. Indeed, the mixed results of previous studies that have used anti-inflammatory therapies in schizophrenia may be a result of not targeting the appropriate patients or the best outcome measures. There are currently no effective treatments for negative symptoms or motivational deficits in schizophrenia, which as noted above represents a significant obstacle to achieving functional recovery, and as such, the discovery of novel therapies are of paramount importance.^{85,86}

[figure not shown]

Figure 1: Working Model of Research Proposal

Working Model

Based on these data, the scientific premise and driving hypothesis of the proposed research is that inflammation decreases activation of ventral striatal reward circuits, leading to decreased objective measures of motivation and ultimately negative symptoms in schizophrenia (see Figure 1 for working model).

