As an amendment to the original protocol, this research also includes computational analysis of language. Recent developments in the automated analyses of language have shown promising findings in identifying computational measures of language to characterize thought disorder in schizophrenia. However, most of the research to date has focused on measure of incoherence and little attention has been paid to other central features of language in schizophrenia such as poverty of content. This additional research protocol aims to measure “semantic density” through the use of machine learning and Natural Language Processing. It also aims to detect latent semantic content reflective of the psychopathology of thought disorder in schizophrenia. The resulting linguistic findings can be potentially analyzed in conjunction with other biomarkers and future findings of the original study.

4. Objectives

Objective 1. Determine the impact of inflammation on reward processing in patients with schizophrenia using functional magnetic resonance imaging (fMRI).

Hypothesis 1: Increased peripheral blood markers of inflammation will be associated with decreased activation of reward-related ventral striatal regions and decreased connectivity between the ventral striatum and medial prefrontal cortex using whole brain analysis.

Dependent variables:

Immune Markers: Peripheral inflammatory markers: plasma CRP, IFN-alpha, IL-6, sIL-6R, IL-10, TNF-alpha, sTNFR 1 and 2, IL-1 beta, IL-1ra, sIL-2R, and MCP-1

Neuroimaging Tasks: Degree of functional connectivity between the striatum and other brain regions on resting state scan (Z scores); performance on fMRI tasks (see below)

Objective 2. Determine the impact of inflammation on objective and clinical measures of motivation and negative symptoms in patients with schizophrenia.

Hypothesis 2: Increased inflammation will be associated with increased impairment in objective and clinical measures of motivation and negative symptoms.

Dependent variables:

Immune Markers: Peripheral inflammatory markers: plasma CRP, IFN-alpha, IL-6, sIL-6R, IL-10, TNF-alpha, sTNFR 1 and 2, IL-1 beta, IL-1ra, sIL-2R, and MCP-1

Behavior: Scores on the: Positive and Negative Symptom Scale (PANSS); Brief Negative Symptom Scale (BNSS); Snaith Hamilton Pleasure Scale (SHAPS); Inventory of Depressive Symptomatology (IDS-SR), Childhood Trauma Questionnaire (CTQ); Motivation and Pleasure Scale (MAPS-SR)

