Neuropsychology: Performance on the Effort Expenditure for Rewards Task (EEfRT), and neurocognitive tasks (see below)

Objective 3. Explore the interrelationship among inflammation, altered reward processing as measured by fMRI, and objective and clinical measures of motivation and negative symptoms in patients with schizophrenia.

Hypothesis 3: Decreased neural activation in reward-related regions will mediate the relationship between inflammatory markers, impaired motivation and negative symptoms.

Immune Markers: Peripheral inflammatory markers: plasma CRP, IFN-alpha, IL-6, sIL-6R, IL-10, TNF-alpha, sTNFR 1 and 2, IL-1 beta, IL-1ra, sIL-2R, and MCP-1

Neuroimaging Tasks: resting state scan; fMRI tasks

Behavior: Positive and Negative Symptom Scale (PANSS); Brief Negative Symptom Scale (BNSS); Snaith Hamilton Pleasure Scale (SHAPS); Inventory of Depressive Symptomatology (IDS-SR); Calgary Depression Scale for Schizophrenia (CDSS), Childhood Trauma Questionnaire (CTQ); Motivation and Pleasure Scale (MAPS-SR)

Neuropsychology: Effort Expenditure for Rewards Task (EEfRT), and neurocognitive tasks (see below)

5. Study Design and Methods

Figure 2: Overview of Proposed Study Visits

Screening Visit Between 9:00 am – 12:00pm	Subject arrives at Grady BHC for consenting and MINI diagnostic interview. They will also complete a physical and psychiatric exam, blood sampling for routine labs, CRP, urine drug screen and pregnancy test. All subjects will be eligible to also complete the MMSE, BNSS, WRAT, and MRI safety screen.
Visit 1	Subjects will be eligible to complete the PANSS, behavioral EEfRT, IDS-SR or SHAPS, and other assessments the PI and study staff may choose from other study visits.
Visit 2 9:00 am	Subject arrives at Emory University Hospital ACTSI suite
9:30 am	Blood Sampling
10:00 am	Behavioral Testing
12:00 pm	Lunch
13:00 pm	MRI Scan
14:30 pm	Complete Study
Visit 3	Complete Behavioral Testing

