Objective 1: The first-level individualized design matrices for each participant will be estimated using a general linear model. Effects of task (see above contrasts) will be computed on a voxelwise basis for each participant in the form of statistical parametric maps of discrete contrasts. Subsequent second level paired t test analyses will be performed on the SPM contrast images. Between-subject effects of task and individual inflammatory marker concentrations (beginning with CRP) will be determined using regression analysis. For the resting state and task based functional connectivity analysis, whole brain, subject-level correlation maps indicating regional similarity with the striatal seed region time series will be generated and Fisher transformed to Z-score maps. In addition, data reduction strategies will be employed to address inflammatory marker collinearity in analyses combining relevant inflammatory markers. To assess significance of correlated activity with each bilateral seed region, paired t-tests will be conducted on participants' Z-score maps, adjusted for multiple comparisons. For significant brain regions, descriptive statistics will be used to characterize the mean, standard deviation, and standard error of the Z scores. Relevant covariates, which may be associated with alterations in functional connectivity or task performance, include body mass index (BMI), age, sex, education, nicotine use, antipsychotic dose (as measured by chlorpromazine equivalents), use of other medications, as well as depression, and will be included in the analyses as appropriate.

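### Hypothesis 3 names neural activation as the mediator, but the Objective 3 analysis tests mediation only through functional connectivity, so the hypothesis as worded has no planned test

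*Combined protocol and SAP*

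**What the plan says.** Section 4, Hypothesis 3, states: "Decreased neural activation in reward-related regions will mediate the relationship between inflammatory markers, impaired motivation and negative symptoms". The working model at the end of section 3 gives the same intermediate step as the driving hypothesis: "inflammation decreases activation of ventral striatal reward circuits, leading to decreased objective measures of motivation and ultimately negative symptoms in schizophrenia".

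The Objective 3 paragraph of section 7 begins "Formal mediation analysis will be conducted to assess whether functional connectivity mediates" the link between inflammatory markers, starting with CRP, and behaviour. No other mediator is named there.

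Hypothesis 1 lists the two imaging quantities side by side as separate predictions: "decreased activation of reward-related ventral striatal regions and decreased connectivity between the ventral striatum and medial prefrontal cortex". The Objective 1 analysis derives them by different routes. For activation, "Effects of task (see above contrasts) will be computed on a voxelwise basis for each participant", and then "Between-subject effects of task and individual inflammatory marker concentrations (beginning with CRP) will be determined using regression analysis". For connectivity, striatal seed correlation maps are Fisher-transformed to Z scores.

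The only imaging-to-behaviour regression for Part A is under Objective 2. It concerns "the relationship between changes in functional connectivity (Z scores) obtained using fMRI and changes in behavior and neuropsychological performance".

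**The concern.** A mediation claim has two links: exposure to mediator, and mediator to outcome given exposure. For activation, Part A plans only the first (inflammatory markers to task activation, Objective 1). Neither the second link nor the indirect effect is planned. Both are directed at connectivity, a different measurement.

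If the plan is followed exactly, Objective 3 will produce a connectivity result that has to be reported against a hypothesis about activation. A null could be written up as evidence against Hypothesis 3, and a positive result as support for it. Neither inference is sound. The choice of imaging measure could also be settled after the results are seen, because the hypothesis and the analysis point to different ones.

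**Working it through.** **Step 1. Search for any other test of activation as mediator.**
- Objective 1: activation is regressed on inflammatory markers. This is the first link only.
- Objective 2: task performance is regressed on inflammatory markers, and behaviour is related to connectivity. Activation does not appear.
- Objective 3: mediation through connectivity. The moderated-mediation model extends the same pathways.
- Part C, Hypothesis 2b: inflammation is the mediator, not activation.

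No planned analysis fills the gap.

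**Step 2. The plan's own power figure.** Section 7 states more than 80% power for r = 0.5 with N = 100, two-tailed alpha 0.05. By Fisher's z, power = Φ(atanh(r)·√(N−3) − 1.96). Here atanh(0.5) = 0.5493 and √97 = 9.849, so the product is 5.410. Then 5.410 − 1.96 = 3.450, and power is 0.9997. The statement is correct, but it concerns a simple correlation and says nothing about an indirect effect through either measure.

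**Step 3. Illustration of what a substituted mediator can miss.** None of these inputs is in the documents; all are assumptions. N = 100, inflammation-to-activation path a = 0.3, activation-to-behaviour path b = 0.4, no direct effect, one marker, one outcome, standardised variables. Connectivity C equals r times activation plus noise, with no effect of its own, and r is shown over a range.

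Under this model:
- corr(inflammation, C) = a·r
- partial corr(C, behaviour given inflammation) = (b·r − ab·a·r) / √[(1 − (ab)²)(1 − (a·r)²)]

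Approximate power is the product of the two-sided powers of the two links, using √(N−3) and √(N−4). For activation itself (r = 1) the first link is 0.30: 0.3095 × 9.849 = 3.048, power 0.862. The second is 0.364/√(0.9856 × 0.91) = 0.384: 0.4052 × 9.798 = 3.970, power 0.978. The product is 0.84.

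For connectivity:

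| r | First link | Second link | Product of powers | Percentile bootstrap |
|---|---|---|---|---|
| 0 | 0 | 0 | 0.05 × 0.05 = 0.003 | 0.001 |
| 0.3 | 0.090 | 0.110 | 0.144 × 0.192 = 0.028 | 0.019 |
| 0.5 | 0.150 | 0.185 | 0.319 × 0.452 = 0.144 | 0.125 |
| 0.7 | 0.210 | 0.263 | 0.556 × 0.750 = 0.417 | 0.417 |

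The bootstrap column is the share of 1,500 simulated trials (800 resamples each) whose 95% interval excludes zero. The activation test gave 0.838 to 0.861 in the same runs.

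**Step 4. The reverse case.** If connectivity is the sole mediator and activation is unrelated to it, the roles swap. The planned test is positive in about 84% of trials and an activation test in about 0.1%. Reporting the planned result as confirming Hypothesis 3 would then be wrong.

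**Step 5. The Objective 2 wording.** The Part A schedule of assessments (Figure 3) places the MRI at Visit 2 only. One scan gives no change in connectivity, so the sentence cannot be carried out literally in Part A. The mediator-to-behaviour link for connectivity therefore needs correcting too.

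**The case against.** The strongest defence is that the wording is loose and connectivity was always intended. Aim 3 in the abstract speaks of reward circuitry. Objective 3 speaks of reward processing measured by fMRI and lists both the resting scan and the fMRI tasks. The background uses neural activity in reward circuits to summarise evidence that includes a connectivity study. Objective 3 is also labelled exploratory. This stands in part: the broad aim is addressed by connectivity, and the exploratory label lowers the stakes. It does not supply a test of Hypothesis 3, because Hypothesis 1 and the Objective 1 analysis keep the two measures apart. Connectivity computed from task scans is still connectivity.

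The second objection is that the percentages follow from the assumptions. That is right. The near-zero rate at r = 0 is true by construction, and connectivity is given no effect of its own, although the background reports CRP associated with connectivity in depression.

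A reader might also infer that the high-versus-low inflammation moderator would be CRP split to moderate CRP. The Objective 3 paragraph names no marker or cut-off, so that remains a guess, and no weight is put on it here.

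**Conclusion.** The mismatch is real and can be checked by setting Hypothesis 3 beside the Objective 3 analysis. Followed exactly, the plan does not test Hypothesis 3, and no Part A analysis relates task activation to behaviour.

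The size is limited. A reader might infer that Objective 3 as a whole is untested, or that the trial's power for mediation falls from about 85% to somewhere between 0 and 42%. The documents support neither reading. Connectivity partly serves the exploratory aim, and those figures rest on an assumed N of 100, paths of 0.3 and 0.4, activation as the only mediator, and an assumed correlation between the two measures. They show that testing one variable can miss an effect carried by another; they do not estimate this trial's loss. The point deserves correction before analysis but does not threaten the study as a whole.

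**What to change.** Before analysis, do one of two things.

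(a) Add ventral striatal activation as a mediator, taken from one named task contrast, in participants scanned on that task. One candidate is reward anticipation in the MID task, of whose anticipatory delay the protocol says "This epoch has repeatedly been associated with robust ventral striatal activity", averaged over the 6 mm ventral striatal sphere already defined for the seed analysis. The contrast must be written out, because the Objective 1 text refers back to contrasts that are not listed. Keep connectivity as a separate mediator, and state that a connectivity result does not confirm the activation hypothesis.

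(b) If activation was not intended, reword Hypothesis 3 to functional connectivity. This is the cheaper course, though the driving hypothesis in section 3 would then remain broader than what is tested.

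Under either option, replace the reference to changes in connectivity and behaviour under Objective 2 with single-visit values for Part A.

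The cost is plan wording and, under (a), one more exploratory model with no added procedures. The usable sample may be below 100, since the protocol lets the investigator choose one or two fMRI tasks and omit imaging for some participants. Under the same assumed paths, an activation test with 60 scanned (an assumed number) has roughly 56% power, against about 85% at 100. A null from it should be reported with its confidence interval and not as a refutation.
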